PROTOCOL TITLE:

Usability and acceptability of virtual reality-based cognitive stimulation by healthy participants

PRINCIPAL INVESTIGATOR

[name]/Department of Surgery

CO-INVESTIGATORS/ COLLABORATORS:

[name] / Neurologist

[name]/Statistician

[name], EnMED student

SPONSOR / FUNDING AGENCY

Houston Methodist Hospital

Reliant Innovation grant

VERSION NUMBER/DATE

v.1: 05 JUN 2022

REVISION HISTORY

Revision #	Version Date	Summary of Changes	Consent Change (Yes/No)

1. Study Summary

Virtual reality (VR) imitates reality by creating an artificial 3-D environment using computing technology or software. Using this software with a headset, a virtual environment is created, which cognitively stimulates the user's brain to think they are in an artificial world. Creating a virtual environment allows flexibility and measurement of different types of stimuli while recording the various responses provided by users in the controlled virtual environment. VR strengthens the brains' ability to focus, learn, and retain experience. VR for attention deficit disorders has been reported to have promising results. We plan to follow in similar footsteps using the gamification of exercises for cognitive stimulation in healthy volunteers to record outcomes and usability testing.¹ These exercise "games" allow users to focus and pay attention to the game while helping reorient and cognitively stimulate the user's brain. The games are built with increasing difficulty and complexity of user demand and output. Our team developed a

novel, 3D simulated software platform prototype called ReCognition VR to provide VR-based cognitive exercises to healthy participants for testing.

Our premise is that VR-based cognitive stimulation software will allow controlled delivery of structured cognitive exercises focusing on orientation, attention, memory, and executive functions. The system will allow customized frequency and duration of cognitive exercises based on the users' difficulty level in a delightfully relaxed- environment with music.

Hypothesis:

We will test the hypothesis that VR-based cognitive exercise will be feasible and acceptable by the test population.

2. Purpose of the Study / Objectives

The purpose of this study is to determine the feasibility, acceptability and usability, and to assess the safety of use of a VR-based software in health volunteers. Results from this study will be used to inform the design of a future study in hospitalized patients at risk for delirium.

The question that drives this study is:

In healthy volunteers, what is the feasibility of use of the ReCognition VR-based software and what is the acceptability and usability of the software?

OBJECTIVES AND ENDPOINTS

OBJECTIVES	ENDPOINTS	JUSTIFICATION FOR ENDPOINTS
Primary		
The primary objective of this study is to assess the feasibility of VR-based cognitive stimulation exercises in healthy volunteers.	The primary endpoint is use of the ReCognition VR-based software for 20 minutes by 70% of enrolled participants.	It is important to know if participants can complete the exercise since an incomplete experience will prohibit assessment of the other variables to be measured.
Secondary		
The secondary objectives are 
 to determine the acceptability and usability of VR-based cognitive stimulation exercises 	The secondary endpoints are: 
 Acceptability and usability: the proportion of participants with a System Usability Scale (SUS) score >35. 	Successful implementation depends on the acceptability of the intervention and is one of the main factors considered before adopting and

OBJECTIVES	ENDPOINTS	JUSTIFICATION FOR ENDPOINTS
	
 • Proportion of participants who complete the game without any user errors • Number of attempts to complete the game. 	implementing computerized cognitive software.
Tertiary/Exploratory		
Tertiary objectives are to report the safety of VR-based cognitive stimulation exercises in healthy volunteers.	
 • Safety will be assessed using each of the following endpoints: 
 1. Mean change from pre to 10 minutes: 
 a. Heart rate variability: b. Pulse oximetry oxygen saturation (SpO₂) c. Respiratory rate d. Blood pressure 2. Mean change from pre to end of VR session: 
 a. Heart rate variability: b. Pulse oximetry oxygen saturation (SpO₂) c. Respiratory rate d. Blood pressure 	Knowing the proportion of change in these biometric measures will assist in designing future investigation of patients at risk of delirium

3. Background

Attention is the most crucial cognitive domain required for the effective completion of mentally challenging tasks by healthy individuals. Many healthy people cannot complete high executive brain functioning tasks due to lack of focus or attention, leading to poor performance both at work and home. Generally, mild attention deficit is not identified, and daily life stresses are usually blamed. Computerized cognitive training programs have shown improved attention deficit disorder and mild cognitive impairment. Virtual Reality (VR) is an emerging technology and can improve brain functions, including attention. VR engages multiple learning systems, making it a more effective natural environment for cognitive training. Based on this idea, our team developed a 3D simulated software platform prototype called ReCognition VR with incorporated exercise in the forms of games that can improve attention and executive functions.

Recognition VR software (Figure 1) allows users to immerse themselves in a relaxing virtual environment; reorient the user to person, time, and location; and play mini-games to encourage attention, focus, and movement of limbs; and record user progress and scores in mini-games.

Critical gaps exist in our knowledge of cognitive interventions and their application through VR. Data on interventions focused on early cognitive exercise using Virtual Reality Simulation, specifically using Oculus Quest 2 and Unity software, are limited. Moreover, many critical barriers to implementing cognitive exercise in clinical protocols exist. Cognitive stimulation through VR is a new and upcoming area in technology that is rapidly expanding but currently limited in the literature. A lack of understanding or appreciation for the evidence supporting cognitive stimulation through VR, specifically gamification, contributes to the barriers. The rapid increase and use of VR in other areas urges our team to seek this area for development.

The major goals of this proposal are to assess the feasibility and usability of VR-based cognitive interventions in healthy volunteers using ReCognition VR software while providing easy delivery of cognitive stimulation exercises provided by VR.

4. Study Design

The study is a single-center, prospective assessment of the feasibility, acceptability and usability of ReCognition VR -based simulated cognitive stimulation to improve attention and focus in healthy participants.

Sample size: We will enroll 30 participants: 15 participants who are >18 or up to 35 years of age and 15 participants who are >60 years of age. Results from each age group will be analyzed separately.

Justification of sample size: The study is a feasibility study having the expectation that 70% of participants in each group (>18-35 years of age and >60 years of age) will complete 20 minutes of the ReCognition VR-based exercise and where each group will be evaluated separately. Descriptive statistics will be used to summarize the findings; 15 participants in each group will be recruited. The intent is that this study will provide information for a larger, subsequent clinical trial of patients >60 years old at risk for delirium.

Data and measures to be taken:

The endpoints for this feasibility study are:

Primary – 70% of participants in each group will complete 20 minutes of use of the ReCognition VR-based software (a binary outcome).

[figure not shown]

Figure 1: Describes the system architecture to the observer and healthy participants

Secondary – We will measure the acceptability and usability of the experience based on the proportion of participants with a System Usability Scale (SUS) score >35.

We will report on the proportion of participants who complete the game without any user errors

We will report on the number of attempts each participant uses to complete the game.

We will examine measure that can inform on safety of the experience to be used in the subsequent clinical trial. The measures are:

1. Mean change from pre to 10 minutes of the ReCognition VR-based exercise in:
 - a. Heart rate variability:
 - b. Pulse oximetry oxygen saturation (SpO₂)
 - c. Respiratory rate
 - d. Blood pressure
2. Mean change from pre to end of the ReCognition VR-based exercise in:
 - a. Heart rate variability:
 - b. Pulse oximetry oxygen saturation (SpO₂)
 - c. Respiratory rate
 - d. Blood pressure

We will report the demographic variables of age, sex, race and ethnicity for each group and the clinical characteristics whereby they meet ASA criteria (body mass index, self-reported history of hypertension with active management, drinking status, and smoking status; see Section 9).

Accessing data from medical records:

This feasibility study involves healthy volunteers. No medical records will be reviewed. Medical history will be self-reported.

Data analysis plan:

The results of this study will be reported using descriptive statistics. Continuous variables will be reported as means with standard deviation or medians and interquartile range contingent on normality of the distribution. Categorical variables will be reported using Chi-square or Fisher's exact test, as appropriate.

5. Study Intervention

1. The healthy participants will be selected from a random population to use the Recognition VR – based cognitive exercise interventions.
2. The study participants will receive a 3D- ReCognition VR-based simulated cognitive exercise program targeting attention, organizing thinking, motor activities, and executive brain functions.
3. The study team will create an order set for the 3-D Recognition VR – based cognitive stimulation exercise sessions to be delivered to the healthy participants who will place virtual reality headsets on themselves.
4. The detail of the software as follows:

3-D Recognition Virtual Reality-Based Simulation Sessions Program:

Software Platform:

Virtual reality platform will consist of

- The virtual reality headsets manufactured by the Oculus Quest 2 glasses (Facebook inc., USA) with stereoscopic vision and stereo sound will be used to show the virtual world to participants.
- Motion Sensor
- Flat Screen TV with Software

The virtual reality headsets manufactured by the Oculus Quest 2 glasses (Facebook inc., USA) with stereoscopic vision and stereo sound will be used to show the virtual reality to study participants. After headset placement, the study participants will be able to follow instructions provided by virtual nurse AVATAR. The participants will receive low cognitive load exercises based on virtual reality techniques, including a relaxed environment, music therapy, time orientation, delivery instructions, and task completion motivation. The exercise task will focus on attention, organized thinking, motor activities, and executive brain functions.

Dosing:

The study participants will receive approximately 20 minutes of VR- based cognitive stimulation session and fill out a post-user survey.

The session will provide neurocognitive stimulation, engagement through exercise.

The physiological data of vital signs will be recorded before, during, and after sessions (see Schedule of Activities).

Acceptability Survey:

PI or a research team member will interview the healthy participants using the System Usability Scale survey.

The estimated date to complete the study is **one month** after the last participant is enrolled.

Schedule of activities

Procedures	Day 1, Time 1: pre	Day 1, Time 2: 10 minutes	Day 1, Time 3: post	Day 1, Time 4: end of study
Informed consent	X			
Demographics	X			
Medical history	X			
Administer study intervention		-----X-----		
Concomitant medication review	X			
Physical exam (including height and weight)	X			

Procedures	Day 1, Time 1: pre	Day 1, Time 2: 10 minutes	Day 1, Time 3: post	Day 1, Time 4: end of study
Frailty assessment	X			
Heart rate variability	X	X	X	
Pulse oximetry	X	X	X	
Respiratory rate	X	X	X	
Blood pressure	X	X	X	
System User Survey				X
Adverse event review and evaluation				X
Complete Case Report Forms (CRFs)	X			X

6. Drugs, Biologics, Devices

Specifically, VR will be simulated using UNITY software and Oculus quest (two headsets) for this project.

7. Collaborative / Multi-site Research

N/A

8. Data Privacy / Confidentiality

Houston Methodist policies for Protected Health Information (PHI) will be followed, including all physical and electronic data security requirements, encrypted devices, and HM password-protected servers.

All data obtained for the study will be stored in a password-protected spreadsheet in a Methodist server and will only be accessible to IRB-approved investigators and research staff at Houston Methodist. Data will be completely de-identified at the time of collection and sent to the statistician via secure mail for analysis. Research materials will be stored in a password-protected computer system database on a secure server on the Houston Methodist network. Data collected will be transferred and stored on RedCap, a secure web application for building and managing databases. Study personnel requiring access will have their own Login/Password. Access to clinical study information will be based on individuals' roles and responsibilities. All study data will be transmitted over an encrypted SSL (Secure Sockets Layer) connection that requires user authentication. This application is designed to be in full compliance with the International Conference on Harmonization and Good Clinical Practices (ICH-GCP), the FDA's Code of Federal Regulations (CFR) 21 Part 11 Electronic Record and Electronic Signatures, the

FDA's "Guidance: Computerized Systems Used in Clinical Trials," and the Privacy Rule of the Health Insurance Portability and Accountability Act of 1996 (HIPAA).

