This study will be a single-center study of healthy volunteers conducted at Houston Methodist Hospital. We will enroll 15 participants who are >18 and <35 years of age and 15 participants who are ≥60 years of age. The rationale for the age distribution is to obtain information from people who are considered healthy by ASA criteria 1 and people who meet ASA criteria 2. Participants who are >18 to 35 years of age are a) more likely to have experienced VR software previously and b) more likely to meet ASA criteria 1. Participants who are >60 years of age are a) less likely to have experienced VR software previously and b) more likely to meet ASA criteria 2. These older participants are considered similar to the target population of a proposed subsequent conventional clinical trial; however, it is possible that participants in the younger age group (>18 to 35 years of age) may meet ASA criteria 2.

A total of 30 participants will be prospectively enrolled. All participants will be given post-use surveys to assess usability and efficacy outcomes.

Inclusion Criteria:

1. Healthy volunteers >18 years of age who meet one of the following criteria:
 - a. **ASA 1:** A normal healthy patient. Example: Fit, nonobese (BMI under 30), a nonsmoking patient with good exercise tolerance.
 - b. **ASA 2:** A patient with mild systemic disease. Example: Patient with no functional limitations and a well-controlled disease (eg, treated hypertension, obesity with BMI under 35, frequent social drinker, but is nonsmoking).
2. Person without underlying cognitive disorder or associated phobias (eg. claustrophobia).

Exclusion Criteria:

1. Person with active psychiatry disorders, especially schizophrenia
2. Person who is deaf or blind.

11. Screening and Recruitment

All participants will be screened by the principal investigator and clinical research staff, who have been trained in the clinical investigational plan, to determine if the potential participant is eligible for enrollment. Potential participants will be assigned a screening number which will be recorded in an excel sheet; all participants who receive the study intervention during the study will be noted. All participants must meet eligibility criteria (and if not, which eligibility criteria were not met will be recorded); reasons for not meeting enrollment criteria or receiving study intervention will be recorded. No participants belonging to a vulnerable population will be enrolled.

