During the informed consent process, the investigator or designee, who has been trained on the protocol, will explain the nature and scope of the intervention, potential risks, and benefits of

participation and answer questions from the potential participants. All participants will sign and date the Institutional Review Board (IRB)/Ethics Committee (EC) approved informed consent form before any study-specific procedures are performed. In addition, the signed informed consent will be retained with the research records, and a copy will be given to the participant.

Healthy Participants will be identified:

1. Through public advertisement sent via flyers posted around Texas Medical Center and mass emails to public domain emailing lists for example, University of Houston and Rice University, available to the local Houston population.

No medical records will be reviewed for this healthy volunteer study. Medical history obtained will be from participant self-report.

12. Withdrawal of Subjects

Participants will be withdrawn from the study if they do not receive any study interventions. At the moment of withdrawal, all data related to participant will be removed from the corresponding excel documents and waivers will be shredded.

A participant may discontinue his or her participation without giving a reason at any time during the study. For example, the Principal Investigator may withdraw a participant due to failure to comply with pilot study intervention requirements, or the participant is uncooperative or refuses to continue in the study intervention.

13. Provisions to Protect the Privacy Interests of Subjects

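### The objectives table sets the primary endpoint at 70% of enrolled participants while Section 4 sets it at 70% in each age group; align the table with Section 4 and report each group with an exact interval

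*Combined protocol and SAP*

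**What the plan says.** Section 2 (Objectives and Endpoints) gives the primary endpoint thus: "The primary endpoint is use of the ReCognition VR-based software for 20 minutes by 70% of enrolled participants". No age group is named.

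Section 4 (Study Design) gives it per group: "70% of participants in each group will complete 20 minutes of use of the ReCognition VR-based software (a binary outcome". Two other statements in Section 4 agree. The sample size paragraph says "Results from each age group will be analyzed separately", and the justification expects 70% in each group, "where each group will be evaluated separately". Enrolment is 15 per group, 30 in all. The stated intent is that "this study will provide information for a larger, subsequent clinical trial of patients >60 years old at risk for delirium".

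The data analysis plan at the end of Section 4 is descriptive. For proportions it says only "Categorical variables will be reported using Chi-square or" Fisher's exact test. It names no comparison and no interval.

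Section 12 (Withdrawal of Subjects) says "Participants will be withdrawn from the study if they do not receive any study interventions", and then that data are removed at withdrawal.

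**The concern.** Two current statements of the primary endpoint give different criteria, and the more lenient one stands in the table where a reader looks first for the endpoint. If 11 of 15 younger and 10 of 15 older participants complete, the total is 21 of 30, exactly 70%. The table's wording would allow this to be reported as the endpoint met. Section 4 would report it as met in the younger group and not met in the older group.

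The older group is the one to be carried forward to the later trial. Section 10 also gives a reason why it might do worse: "Participants who are >60 years of age are a) less likely to have experienced VR software previously".

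A smaller reporting gap goes with this. Chi-square and Fisher's exact test compare groups. They do not describe one group's completion proportion or set it against 70%.

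**Working it through.** **Inputs.** 15 participants per group, 30 in total and a 70% criterion (Sections 2 and 4). An expected rate of 70% in each group (Section 4) is the only rate the documents give; all other true rates below are assumptions. The documents state no alpha, power, null rate or precision target, so there is no sample size derivation to reproduce beyond 15 + 15 = 30.

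**Cut-offs.**
- Section 2 read literally: 0.70 × 30 = 21, so at least 21/30.
- Section 4: 0.70 × 15 = 10.5, so at least 11/15 (73.3%) in each group; 10/15 is 66.7%.

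**Direction.** If both groups reach 11, the total is at least 22, which exceeds 21. Section 4 therefore cannot be met with Section 2 missed; only the reverse can happen.

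**Probability that the literal Section 2 rule passes while the older group is below 11.** Let Y and O be independent binomial counts with n = 15 (younger, older). Sum P(O = k) × P(Y ≥ 21 − k) over k ≤ 10. At 70%/70%:

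| Older count k | P(O = k) | P(Y ≥ 21 − k) | Product |
|---|---|---|---|
| 10 | 0.2061 | 0.5155 | 0.1063 |
| 9 | 0.1472 | 0.2969 | 0.0437 |
| 8 | 0.0811 | 0.1268 | 0.0103 |
| 7 | 0.0348 | 0.0353 | 0.0012 |
| 6 | 0.0116 | 0.0047 | 0.0001 |

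The unrounded sum is 0.1615. The share at 10/15, one participant short, is 0.1063 / 0.1615 = 66%.

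**Across true rates (younger/older).**

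| Rates | P(total ≥ 21) | P(both ≥ 11) | P(total ≥ 21, older < 11) |
|---|---|---|---|
| 70/70 | 0.589 | 0.266 | 0.16 |
| 80/80 (assumed) | 0.939 | 0.699 | 0.12 |
| 90/90 (assumed) | 0.9995 | 0.975 | 0.01 |
| 80/70 (assumed) | 0.805 | 0.431 | 0.31 |

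The unequal case is shown because Section 10 expects less VR experience in the older group.

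**Precision of a per-group result (Clopper-Pearson 95%).** 11/15: 44.9% to 92.2%. 10/15: 38.4% to 88.2%.

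**What the named tests would show.** If each group had 8/15 (53%), a Fisher comparison gives p = 1.00 although both groups miss 70%.

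**Denominator.** If one enrolled participant in a group receives no intervention and the data are removed, 14 remain. Then 10/14 = 71.4% meets 70%, while a fixed count of 11 would not be met. The criterion should therefore be a percentage of a stated denominator.

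**The case against.** The strongest reply is that the documents largely settle the matter themselves. Section 4 gives the per-group reading three times, and no section describes a pooled analysis. The Section 2 table names no age groups for any endpoint, so it can be read as a summary. The study is descriptive, with no go/no-go rule, and a reader shown both groups' counts could form a correct view. At 70%/70%, an older group at 9/15 or fewer alongside a literal pass has probability of only about 0.055 (0.1615 − 0.1063). All of this stands. It limits the point to aligning the wording.

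Three stronger readings are tempting, and the documents do not support them.

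- A reader might infer that a split result has no defined report. Separate evaluation already implies one: met in one group, not met in the other.
- A reader might infer that participants who stop early would be dropped from the denominator. The data-removal sentence sits in the paragraph about participants who received no intervention. Stopping early is covered in the next paragraph, which has no removal instruction.
- A reader might infer that the plan tests the 70% target with Chi-square or Fisher's exact test. The sentence is generic and is not assigned to that target. The 8/15 example shows only that these tests cannot serve as the description of a proportion.

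The interval is likewise an improvement in reporting. It corrects no figure, because the plan promises no precision.

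**Conclusion.** The inconsistency is real and should be fixed. Section 4 should govern. If the Section 2 wording is taken literally, the endpoint can be met while the over-60 group misses 70%, with probability 0.16 at 70%/70%. Under the assumed rates this ranges from 0.01 (90/90) to 0.31 (80/70). These figures assume independent groups of 15 with everyone counted, and they apply only to the literal reading.

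A reader might infer that the sponsor plans a pooled analysis or that an error rate is inflated. Neither follows: no pooled analysis is described and no hypothesis test of the 70% target is planned. What is at stake is which result is reported as feasible for the age group of the next trial.

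Confidence is high on the wording conflict and on the gap in describing proportions. It is low on the denominator, which is a minor clarification.

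**What to change.** 1. Reword the primary endpoint in Section 2 to match Section 4, for example: *at least 70% of participants in each age group complete 20 minutes, assessed and reported separately for each group; no pooled pass is claimed.* Add that with 15 in the denominator this means at least 11, and use the same sentence in Section 4.
2. In the data analysis plan in Section 4, for the primary and binary secondary endpoints, replace the Chi-square/Fisher sentence with n/N, percentage and exact (Clopper-Pearson) 95% confidence interval per age group.
3. As a minor clarification, state one denominator for the primary endpoint, reconciling the word enrolled in Section 2 with the removal of untreated participants' data in Section 12. Confirm that anyone who starts a session and stops before 20 minutes counts as not completing.

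The cost is wording in Sections 2, 4 and 12, with no added participants, visits or data. The drawbacks are that the reported precision looks less favourable and that a pooled pass cannot be claimed when one group falls short.

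### The plan is inconsistent on whether early stoppers can be assessed and gives the SUS proportion no denominator, so acceptability could be overstated if they are left out and score worse

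*Combined protocol and SAP*

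**What the plan says.** All references are to the combined protocol and SAP.

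- **Section 2, table of objectives and endpoints.** The primary endpoint is "use of the ReCognition VR-based software for 20 minutes by 70% of enrolled participants". The justification column explains the choice by saying that "an incomplete experience will prohibit assessment of the other variables to be measured". The secondary endpoint for acceptability and usability is "the proportion of participants with a System Usability Scale (SUS) score >35". Section 4 repeats that wording.
- **Section 4.** "15 participants in each group will be recruited", 70% of each group is expected to complete 20 minutes, and "Results from each age group will be analyzed separately". The data analysis plan is descriptive. It names no analysis set and gives no rule for a missing SUS.
- **Section 5.** The dosing text describes a session of about 20 minutes followed by a survey. The Schedule of activities has the survey once, in the column "Day 1, Time 4: end of study", and does not say what happens after an early stop.
- **Section 10.** "All participants will be given post-use surveys to assess usability and efficacy outcomes".
- **Section 12.** A participant who receives no intervention is withdrawn, and at withdrawal that person's data are removed. The next paragraph gives refusal to continue the intervention as an example of withdrawal by the investigator.
- **Section 14.** A session is also stopped when vital signs change by more than 20% from baseline.

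**The concern.** The Section 2 sentence is the plan's only statement about assessing people who do not finish. Taken literally, it puts the SUS out of reach for them, whereas Section 10 gives everyone the survey. The primary endpoint is counted over enrolled participants, but the SUS endpoint refers only to participants. The choice between completers and all starters is therefore open and could be made after the results are known.

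A completers-only proportion selects on tolerance of the system. People who stop because they dislike it or cannot use it might well score low, and their absence would then flatter the result. Acceptability is part of the study hypothesis in Section 1, and Section 4 says the study is to inform a larger trial in patients over 60. The SUS has a single scheduled time point, so a score not taken on the day may be lost.

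**Working it through.** **Inputs from the documents.** n = 15 per age group, analysed separately, with a completion target of 70% (Section 4). The plan gives no error rates, precision target or SUS data by completion status, so there is no SUS figure of its own to reproduce. Its totals agree: 15 + 15 = 30.

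**Early stopping compatible with the target.** 0.70 × 15 = 10.5, so at least 11 must complete. Up to 15 − 11 = 4 people per group can stop early with the primary endpoint still met.

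**Assumptions.** All 15 enrolled start the session, and the SUS counts below are illustrative.

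**Formulas.** Let c be completers, s = n − c early stoppers, x completers scoring above 35, and k stoppers who score, or would score, above 35.

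- Completers-only proportion: x/c
- All-starters proportion: (x + k)/n
- Difference: x/c − (x + k)/n = (s/n) × (x/c − k/s)

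The last form shows what drives the result. The difference is positive only if the stoppers' rate k/s is below the completers' rate x/c, zero if the two are equal, and negative if the stoppers' rate is higher. It cannot exceed s/n.

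**Results per age group.**

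| c of 15 | x | k | Completers only | All starters | Difference (points) |
|---|---|---|---|---|---|
| 11 | 11 | 0 of 4 | 11/11 = 100% | 11/15 = 73.3% | +26.7 |
| 11 | 11 | 2 of 4 | 100% | 13/15 = 86.7% | +13.3 |
| 11 | 11 | 4 of 4 | 100% | 15/15 = 100% | 0 |
| 11 | 9 | 0 of 4 | 9/11 = 81.8% | 9/15 = 60.0% | +21.8 |
| 11 | 9 | 2 of 4 | 81.8% | 11/15 = 73.3% | +8.5 |
| 11 | 9 | 4 of 4 | 81.8% | 13/15 = 86.7% | −4.8 |
| 13 | 13 | 0 of 2 | 13/13 = 100% | 13/15 = 86.7% | +13.3 |
| 13 | 13 | 2 of 2 | 100% | 15/15 = 100% | 0 |

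Check of the extreme row by the third formula: (4/15) × (1 − 0) = 0.267.

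**Precision.** Exact (Clopper-Pearson) 95% intervals are 71.5% to 100% for 11/11 and 44.9% to 92.2% for 11/15. They overlap, as intervals at this sample size will. The shift in the extreme row is nevertheless a bias from selection, and an interval around the completers-only figure does not account for it.

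**The case against.** The strongest reply is that the Section 2 sentence is a rationale, not a procedure. It explains why completion is the primary endpoint, does not mention the SUS, and tells nobody to withhold it. The operational text is unconditional: Section 10 covers all participants, Section 5 has the team interview participants, the endpoint is a proportion of participants, and the survey column is tied to the end of the study on Day 1, which someone who stops at minute 6 can still reach. This stands. A reader might infer that the plan excludes early stoppers from the SUS; no section says so, and the plain reading leans towards including them.

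The sentence is also true for some measures. A participant who stops before minute 10 has no change from pre-session to 10 minutes in the vital signs. This stands too, and is a reason to narrow the sentence rather than delete it.

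Nor does every stop reflect dislike. A stop under the Section 14 vital-sign criterion need not say anything about usability, so the stoppers' SUS rate cannot be presumed low.

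Finally, counting every missing SUS as not above 35 in the main analysis would score a participant stopped for safety, with no survey, as finding the system unacceptable. That is a reason to keep this rule as a sensitivity analysis.

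What the reply does not remove is the conflict between Sections 2 and 10 or the missing denominator.

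**Conclusion.** The inconsistency is real and the SUS denominator is undefined. The consequence is conditional: the proportion above 35 could be overstated if early stoppers are left out and score worse than completers. At 11 of 15 completing, the difference runs from 0 to +26.7 points if all 11 completers score above 35, and from −4.8 to +21.8 points if 9 of 11 do. The top of that range assumes that none of the four stoppers would score above 35. It is specific to 11 of 15 completing: the bound is s/n, so it is smaller with fewer stoppers and larger if completion falls short of the target.

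Two stronger conclusions are tempting. One is that acceptability is overstated as planned; the documents contain no SUS data by completion and no rule that drops stoppers. The other is that the older group in particular is affected; Section 4 expects the same 70% completion in both groups, so nothing in the plan separates them on this point.

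Section 12 adds a second possible route to exclusion. Its data-removal sentence directly follows the case of people who received no intervention, so its reach is arguable. Read broadly, it would also remove the SUS of someone withdrawn for refusing to continue.

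**What to change.** 1. **Section 2:** limit the justification sentence to measures that truly need a longer session, such as the 10-minute vital signs, so that it does not cover the SUS.
2. **Section 5, Schedule of activities:** state that the SUS is collected at the end of the session, whatever its length, from everyone who starts.
3. **Section 4, endpoint and data analysis plan:** define the denominator as all starters in each age group. Report the number with a missing SUS beside the proportion, add a sensitivity analysis counting missing as not above 35, and give the completers-only figure as supportive.
4. **Section 12:** reconcile the data-removal rule with the above, so that data from a participant who started and then stopped are not removed from this proportion merely because the session was incomplete.

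The cost is wording in four sections. The survey is already planned, so no procedure is added. The downside is that the reported acceptability may be lower than a completers-only figure.
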